#### **7.4.2 Treatment Beyond Disease Progression**

Not applicable per Protocol Amendment 06.

#### **7.4.3 Management Algorithms for IO and Oncology Agents**

IO agents are associated with AEs that can differ in severity and duration from AEs caused by other therapeutic classes. Early recognition and management of AEs associated with IO agents may mitigate severe toxicity. Management algorithms have been developed from extensive experience with nivolumab, ipilimumab, and their combination to assist investigators in assessing and managing the following groups of AEs:

- Pulmonary
- Gastrointestinal
- Hepatic
- Endocrinopathies
- Renal
- Skin
- Neurological

The clinical nature of AEs noted with each FRACTION-Gastric Cancer study treatment combination and/or nivolumab in combination with ipilimumab will determine the role of the algorithms above for use in toxicities related to its use in this study.

The management algorithms recommended for utilization for IO and non-IO agents are included in [Appendix 6](#) and in each FRACTION-Gastric Cancer Sub-Protocol.

#### **7.4.4 Treatment of Treatment-related Infusion Reactions**

Guidelines for the treatment of study treatment-related infusion reactions for each FRACTION-Gastric Cancer study treatment combination are provided in each FRACTION-Gastric Cancer Sub-Protocol describing that treatment combination.

#### **7.5 Preparation/Handling/Storage/Accountability**

The IP should be stored in a secure area according to local regulations. It is the responsibility of the investigator to ensure that IP is only dispensed to study participants. The IP must be dispensed only from official study sites by authorized personnel according to local regulations.

The product storage manager should ensure that the study treatment is stored in accordance with the environmental conditions (temperature, light, and humidity) as determined by BMS. If concerns regarding the quality or appearance of the study treatment arise, the study treatment should not be dispensed and BMS should be contacted immediately.

Study treatment not supplied by BMS will be stored in accordance with the package insert.

IP documentation (whether supplied by BMS or not) must be maintained that includes all processes required to ensure study treatment is accurately administered. This includes documentation of study treatment storage, administration and, as applicable, storage temperatures, reconstitution, and use of required processes (eg, required diluents and administration sets).

For study treatments not provided by BMS and obtained commercially by the site, storage should be in accordance with the product label. Infusion-related supplies (eg, intravenous bags, in-line filters, and 0.9% NaCl solution) will not be supplied by the Sponsor and should be purchased locally if permitted by local regulations.

Storage facilities for controlled substances must be securely locked and substantially constructed, with restricted access to prevent theft or diversion, as applicable by local regulations.

- Further guidance and information for final disposition of unused study treatment are provided in [Appendix 2](#) and the Pharmacy Manual.

#### **7.5.1 Retained Samples for Bioavailability / Bioequivalence / Biocomparability**

Not applicable.

## **7.6 Treatment Compliance**

Study treatment will be administered in the clinical facility by trained medical personnel. Treatment compliance will be monitored by treatment accountability, as well as by recording administration of each study treatment in the participants' medical records and CRF.

## **7.7 Concomitant Therapy**

### **7.7.1 Prohibited and/or Restricted Treatments**

The following prohibitions and restrictions apply to all FRACTION-Gastric Cancer Sub-Protocols for the FRACTION-Gastric Cancer study. Additional FRACTION-Gastric Cancer Sub-Protocol-specific prohibitions and/or restrictions are outlined in each FRACTION-Gastric Cancer Sub-Protocol.

The following medications are prohibited during the Treatment Phase of the study:

- 1) Immunosuppressive agents (except for those stated in [Section 7.7.3](#)) are prohibited unless they are utilized to treat an AE.
- 2) Chronic systemic corticosteroids (prednisone > 10 mg daily or equivalent; except for those stated in [Section 7.7.3](#)) are prohibited unless they are utilized to treat an AE.
- 3) Vaccines (except for those stated in [Section 7.7.3](#)) are prohibited.
- 4) Any medicinal herbal preparations within 2 weeks prior to the first dose of study treatment are prohibited unless prescribed by a treating physician. Use of marijuana and its derivatives for treatment of symptoms related to cancer treatment are permitted if obtained by medical prescription or if its use (even without a medical prescription) has been legalized locally, as long as no drug-drug interactions are outlined in the specific Sub-Protocol.
- 5) Any concurrent anti-neoplastic treatment (ie, chemotherapy; immunotherapy; extensive, nonpalliative radiation treatment; or standard or investigational agents for treatment of GC/GEJ) is prohibited other than those included in the study treatment combinations.

Any concomitant therapies must be recorded on the CRF from screening to follow-up.

### **7.7.2 Other Restrictions and Precautions**

#### **7.7.2.1 Imaging Restriction and Precautions**

It is the local imaging facility's responsibility to determine, based on participant attributes (eg, allergy history, diabetic history, and renal status), the appropriate imaging modality and contrast regimen for each participant. Imaging contraindications and contrast risks should be considered in this assessment. Participants with renal insufficiency should be assessed as to whether or not they should receive contrast and, if so, what type and dose of contrast are appropriate. Magnetic resonance imaging (MRI) contrast should not be given to participants with severe renal insufficiency (eg, estimated glomerular filtration rate < 30 mL/min/1.73 m^2) because of increased risk of nephrogenic systemic fibrosis in this participant population. In these participants, alternative imaging tests or MRI without gadolinium should be considered. In addition, participants are excluded from MRI if they have tattoos, metallic implants, pacemakers,

etc. The ultimate decision to perform MRI in an individual participant in this study rests with the site radiologist, the investigator, and the standard set by the local IRB/IEC.

### **7.7.3 Permitted Therapy**

Participants are permitted the use of topical, ocular, intra-articular, intranasal, and inhalational corticosteroids (with minimal systemic absorption). A brief course (less than 3 weeks) of corticosteroids prophylaxis (eg, contrast dye allergy) or for treatment of nonautoimmune conditions (eg, delayed-type hypersensitivity reaction caused by a contact allergen) is permitted.

- Inhaled or intranasal corticosteroids (with minimal systemic absorption may be continued if the participant is on a stable dose) and adrenal replacement steroid doses of prednisone > 10 mg daily or equivalent are permitted in the absence of active autoimmune disease. Non-absorbed intra-articular steroid injections will be permitted.
- Immunosuppressive agents and the use of systemic corticosteroids are permitted in the context of treating AEs. Participants receiving corticosteroids must be at prednisone < 10 mg daily or equivalent prior to re-initiation of study treatment. Participants may continue to receive hormone replacement treatment.
- The inactivated seasonal influenza vaccine can be given to participants while on treatment without restriction. Vaccines containing live/attenuated virus (e.g., varicella, zoster, yellow fever, rotavirus, oral polio and measles, mumps, rubella [MMR]) are not permitted while on study treatment and until 100 days post the last dose.
- Non-live COVID-19 vaccination is considered a simple concomitant medication within the study. However, the efficacy and safety of non-live vaccines (including non-live COVID-19 vaccines) in participants receiving investigational agents is unknown.

### **7.7.4 Palliative Local Therapy**

Palliative and supportive care for disease-related symptoms may be offered to all participants on the study. Limited radiation treatment or surgery to control isolated lesions is permitted for participants who have investigator-assessed clinical benefit following consultation with the BMS Medical Monitor (or designee).

Participants should not receive study treatment during radiation because the potential for overlapping toxicities with radiotherapy and FRACTION-Gastric Cancer study treatment combinations or nivolumab in combination with ipilimumab is not known. If palliative radiotherapy in short courses and for isolated fields is required to control symptoms not clearly related to disease progression, then study treatment administration should be withheld, if possible, for at least 1 week before radiation and for at least 1 week after its completion. Participants should be closely monitored for any potential toxicity during and after receiving radiotherapy. Prior to resuming study treatment, radio-therapy related- AEs should resolve to Grade  $\leq$  1 or baseline, and participants must meet relevant eligibility criteria as determined by the BMS Medical Monitor (or designee) in discussion with the investigator. The BMS Medical Monitor (or designee) must be consulted prior to re-initiating study treatment in a participant with a dosing delay lasting > 8 weeks from the previous dose.

Details of palliative radiotherapy should be documented in the source records and electronic case report form (eCRF). Details in the source records should include dates of treatment, anatomic site, dose administered and fractionation schedule, and AEs. Symptoms requiring palliative radiotherapy should be evaluated for objective evidence of disease progression. Participants receiving palliative radiation of target lesions will have the evaluation of ORR just prior to radiotherapy, but these participants will no longer be evaluable for the determination of response subsequent to the date palliative radiation occurs.

For participants who need to undergo elective surgery (not tumor related) during the study, it is recommended to hold study treatment(s) for at least 2 weeks before and 2 weeks after surgery, or until the participant recovers from the procedure, whichever is longer. Prior to resuming study treatment, surgically related AEs should resolve to  $\leq$  Grade 1 or baseline, and participants must meet relevant eligibility criteria as determined by the BMS Medical Monitor (or designee) in discussion with the investigator. The BMS Medical Monitor (or designee) must be consulted prior to re-initiating study treatment in a participant with a dosing delay lasting  $> 8$  weeks from the previous dose.

### **7.7.5 Supportive Care Management**

Supportive care management for each FRACTION-Gastric Cancer study treatment combination and, as necessary, is outlined in the FRACTION-Gastric Cancer Sub-Protocol describing that treatment combination.

## **7.8 Treatment After the End of the Study**

At the end of the study, BMS will not continue to provide BMS-supplied study treatment to participants/investigators unless BMS chooses to extend the study. The investigator should ensure that the participant receives appropriate standard of care to treat the condition under study.

## **8 DISCONTINUATION CRITERIA**

### **8.1 Discontinuation from Study Treatment**

Participants must discontinue IP (and non-IP at the discretion of the investigator) for any of the following reasons:

- Participant's request to stop study treatment. Participants who request to discontinue study treatment will remain in the study and must continue to be followed for protocol-specified follow-up procedures as outlined in [Section 2](#). The only exception to this is when a participant specifically withdraws consent for any further contact with him/her or persons previously authorized by participant to provide this information
- Any clinical AE, laboratory abnormality, or intercurrent illness, that, in the opinion of the investigator, indicates that continued participation in the study is not in the best interest of the participant
- Termination of the study by BMS
- Loss of ability to freely provide consent through imprisonment or involuntarily incarceration for the treatment of either a psychiatric or a physical (eg, infectious disease) illness. (Note: Under specific circumstances and only in countries where local regulations permit, a

participant who has been imprisoned may be permitted to continue as a participant. Strict conditions apply and BMS approval is required.)

- Inability to comply with the protocol
- Pregnancy
- Documented disease progression as defined by RECIST v1.1 (see [Appendix 5](#)), unless the participant meets criteria for treatment beyond progression (see [Section 7.4.2](#)) or the participant continues study treatment by entering another track or receiving retreatment (see [Section 5.1.3.3](#))
- Clinical deterioration while receiving active study treatment that, in the opinion of the investigator, indicates that continued participation in the study is not in the best interest of the participant
- Discretion of the investigator
- Protocol-defined reasons for discontinuation (Criteria for permanent discontinuation for each FRACTION-Gastric Cancer study treatment combination and/or nivolumab in combination with ipilimumab are provided in each FRACTION-Gastric Cancer Sub-Protocol.)
- End of study

Refer to [Section 2](#) and the On-treatment Procedural Outline(s) specific to each FRACTION-Gastric Cancer Sub-Protocol for data to be collected at the time of study treatment discontinuation and follow-up and for any further evaluations that can be completed.

In the case of pregnancy, the investigator must immediately notify the BMS Medical Monitor (or designee) of this event. In most cases, the study treatment will be permanently discontinued in an appropriate manner (eg, dose tapering if necessary for participant safety). Please notify the BMS Medical Monitor (or designee) within 24 hours of awareness of the pregnancy. If the investigator determines a possible favorable benefit/risk ratio that warrants continuation of study treatment, a discussion between the investigator and the BMS Medical Monitor (or designee) must occur.

All participants who discontinue study treatment should comply with protocol-specified follow-up procedures as outlined in [Section 2](#). The only exception to this requirement is when a participant withdraws consent for all study procedures, including posttreatment study follow-up, or loses the ability to consent freely (ie, is imprisoned or involuntarily incarcerated for the treatment of either a psychiatric or a physical illness).

If study treatment is discontinued prior to the participant's completion of the study, the reason for the discontinuation must be documented in the participant's medical records and entered on the appropriate CRF page.

Additional study treatment-specific discontinuation criteria are provided in each FRACTION-Gastric Cancer Sub-Protocol.

### **8.1.1 Permanent Discontinuation**

Criteria for permanent discontinuation for each FRACTION-Gastric Cancer study treatment combination are provided in the FRACTION-Gastric Cancer Sub-Protocol describing that treatment combination.

### **8.1.2 Study Treatment Combination Arm Discontinuation Criteria**

In the event that 20% or more of study participants in a novel FRACTION-Gastric Cancer study treatment combination arm of a given track, at any given time, meet any of the toxicity criteria for permanent discontinuation (as described in [Section 8.1.1](#)), then consideration will be given to discontinue that FRACTION-Gastric Cancer study treatment combination arm in that track. This will include early side effects seen with combination agents and longer-term effects such as endocrinopathies. This action will be taken in consultation with the SMB and will consider other pertinent facts in coming to a decision, including the toxicity profile of that combination seen outside FRACTION-Gastric Cancer, participant benefit as measured by anti-tumor response, and comparison to nivolumab in combination with ipilimumab.

Discontinuation of a study treatment combination arm in a given track for any reason will not lead to discontinuation for that combination in all tracks. Safety of all open-label study treatment combination arms in other tracks that contain the same agent (or agents) will be assessed by SMB and the Sponsor. In the event of serious, unexpected, or life-threatening emergent toxicities, relevant study treatment combination arms may then be modified to maintain the safety of participants. Decisions on such steps and the re-initiation of any study treatment combination arms that had been stopped would be made by SMB in consultation with the Sponsor and relevant authorities (eg, IRB/IEC).

### **8.1.3 Post Study Treatment Study Follow-up**

In this study, PFSR is a key endpoint of the study. Post-study follow-up is of critical importance and is essential to preserving participant safety and the integrity of the study. Participants who discontinue study treatment must continue to be followed (in this study or a rollover study) for safety ([Section 5](#)).

## **8.2 Discontinuation from the Study**

Participants who request to discontinue study treatment will remain in the study and must continue to be followed up for protocol-specified follow-up procedures. The only exception to this is when a participant specifically withdraws consent for any further contact with him/her or persons previously authorized by participant to provide this information.

- Participants should notify the investigator of the decision to withdraw consent from future follow-up **in writing**, whenever possible.
- The withdrawal of consent should be explained in detail in the medical records by the investigator, as to whether the withdrawal is from further treatment with study treatment only or also from study procedures and/or posttreatment study follow-up, and entered onto the appropriate CRF page.
- In the event that vital status (whether the participant is alive or dead) is being measured, publicly available information should be used to determine vital status only as appropriately directed in accordance with local law.
- If the participant withdraws consent for disclosure of future information, the Sponsor may retain and continue to use any data collected before such a withdrawal of consent.

### 8.3 Lost to Follow-up

- All reasonable efforts must be made to locate participants to determine and report their ongoing status. This includes follow-up with persons authorized by the participant.
- Lost to follow-up is defined by the inability to reach the participant after a minimum of 3 documented phone calls, faxes, or emails, as well as lack of response by participant to 1 registered mail letter. All attempts should be documented in the participant's medical records.
- If it is determined that the participant has died, the site will use permissible local methods to obtain date and cause of death.
- If investigator's use of third-party representative to assist in the follow-up portion of the study has been included in the participant's informed consent, then the investigator may use a Sponsor-retained third-party representative to assist site staff with obtaining participant's contact information or other public vital status data necessary to complete the follow-up portion of the study.
- The site staff and representative will consult publicly available sources, such as public health registries and databases, in order to obtain updated contact information.
- If, after all attempts, the participant remains lost to follow-up, then the last known alive date as determined by the investigator should be reported and documented in the participant's medical records.

## 9 STUDY ASSESSMENTS AND PROCEDURES

- Study procedures and timing are summarized in the Schedule of Activities in [Section 2](#) and the On-treatment Procedural Outline(s) specific to each FRACTION-Gastric Cancer Sub-Protocol.
- Protocol waivers or exemptions are not allowed.
- All immediate safety concerns must be discussed with the Sponsor immediately upon occurrence or awareness to determine if the participant should continue or discontinue study treatment.
- Adherence to the study design requirements, including those specified in the Schedule of Activities in [Section 2](#) and the On-treatment Procedural Outline(s) specific to each FRACTION-Gastric Cancer Sub-Protocol, is essential and required for study conduct.
- All screening evaluations must be completed and reviewed to confirm that potential participants meet all eligibility criteria before randomization. The investigator will maintain a screening log to record details of all participants screened and to confirm eligibility or record reasons for screening failure, as applicable.
- Procedures conducted as part of the participant's routine clinical management (eg, blood count) and obtained before signing of informed consent may be utilized for screening or baseline purposes provided that the procedure meets the protocol-defined criteria and has been performed within the timeframe defined in the Schedule of Activities in [Section 2](#) and the On-treatment Procedural Outline(s) specific to each FRACTION-Gastric Cancer Sub-Protocol.

## 9.1 Efficacy Assessments

Disease assessment with contrast-enhanced computed tomography (CT)/MRI scans acquired on dedicated CT/MRI equipment is preferred for this study. CT or MRI of the abdomen, chest, pelvis, and all known sites of disease should be performed for tumor assessments.

CT scans should be acquired with 5-mm slices with no intervening gap (contiguous). Should a participant have a contraindication for CT intravenous contrast, a contrast-enhanced MRI of the chest, abdomen, pelvis, and other known sites of disease may be obtained. MRIs should be acquired with slice thickness of 5 mm with no gap (contiguous). Every attempt should be made to image each participant using an identical acquisition protocol on the same scanner for all imaging time points.

MRI or CT brain scans during on-study treatment and follow-up periods are required only if there is a history of brain metastasis or clinically indicated for symptoms that suggest CNS involvement. Surveillance MRI should be performed per standard of care (approximately every 12 weeks or sooner). Participants with a history of bone metastasis should have a bone scan, if clinically indicated.

Assessments will be performed at baseline and at the time points described in each FRACTION-Gastric Cancer Sub-Protocol, up to and including Week 24 during the Treatment Phase or until disease progression per RECIST v1.1 criteria (see [Appendix 5](#)) or confirmed disease progression for participants treated beyond progression (defined as an additional 10% increase in tumor burden volume with a minimum 5 mm absolute increase from time of initial PD assessment [an increase in the sum of diameters of all target lesions and/or the diameters of new measurable lesions compared to the time of initial PD]), discontinuation of study treatment, or withdrawal from the study. Please refer to [Section 2](#) for timing of assessments. Tumor assessments at other time points may be performed if the investigator is concerned about tumor progression. Assessment of response will be outlined for each combination therapy in the specific FRACTION-Gastric Cancer Sub-Protocol. Assessments of PR and CR must be confirmed at least 4 weeks after initial response. Assessment of tumor response will be reported by the investigator for appropriate populations of participants, as defined by RECIST v1.1 criteria (see [Appendix 5](#)) for participants with solid tumors. Same modality/scanner should be used for all assessments.

Changes in tumor measurements and tumor responses will be assessed by the investigator using RECIST v1.1 criteria. Investigators will also report the number and size of new lesions that appear while on study. The time point of tumor assessments will be reported on the CRF based on the investigator's assessment using RECIST v1.1 criteria. (See [Appendix 5](#) and [Section 7.4.2](#) for specifics of RECIST v1.1 criteria to be utilized in this study.)

Tumor assessments will be submitted to a third party radiology vendor on an ongoing basis; participant management is not dependent on third-party review of tumor assessments.

As a participant's response to prior therapy is an important part of medical history, additional details regarding the previous therapy, including but not limited to best response to therapy, timing of progression on prior therapy, method of how the progression was measured, existence of

confirmation scan to document progression and detailed information such as other clinical evidence (eg, increased pain requiring palliative radiotherapy) to support progression, response/progression dates, and reason for discontinuation will be collected in this trial.

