## **2 SCHEDULE OF ACTIVITIES**

Study assessments and procedures are presented in [Table 2-1](#) (Screening Procedural Outline), [Table 2-2](#) (Baseline for Re-randomization Procedural Outline), and [Table 2-3](#) (Follow-up Procedural Outline). The On-treatment Procedural Outline(s) and exceptions for study treatment combination arms are included in each Fast Real-time Assessment of Combination Therapy in Immuno-ONcology (FRACTION)-Gastric Cancer Sub-Protocol.

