**Table 2-3: Follow-up Procedural Outline**

Procedure	Safety Follow-up a			Notes
	FU 1 30 Days (± 7 Days)	FU 2 60 Days (± 7 Days)	FU 3 100 Days (± 7 Days)	
Patient-reported Outcomes Assessment c	X	X	X	EQ-5D-3L and GaCS and/or ECS Can be collected by telephone at regularly scheduled times
Collection of Survival Status and Subsequent Treatment Information c	X	X	X	Safety follow-up visits must occur in the office. Response (and survival) follow-up visits may be performed by telephone contact or clinic visit.

a FU visits at 30, 60, and 100 days (± 7 days) should occur after the last dose of study treatment or coinciding with the date of discontinuation ± 7 days, if the date of discontinuation is greater than 30 days after the last dose, to monitor for AEs.

b Not applicable as of Protocol Amendment 06: Additional survival follow-up will be collected every 6 months for 3 additional years (2 years of response follow-up + 3 years of survival follow-up = total of 5 years of follow-up). BMS may request that survival data be collected on all treated/randomized participants outside of the protocol-defined window. At the time of this request, each participant will be contacted to determine their survival status unless the participant has withdrawn consent for all contacts or is lost to follow-up. Withdrawal of consent must be clearly documented. See [Section 5.1.3.3](#) for details.

c As of Protocol Amendment 06: Assessments necessary for monitoring safety (eg, safety labs, oxygen saturation, vital signs, physical exams, review of concomitant medications, AE/SAE reporting, etc) will continue per sub-protocol until the FU 3 visit. Tumor Scans, survival status follow-ups, and collection of subsequent treatment information will end once the participant has disease progression, or treatment discontinuation for any reason, whichever occurs first. Collection of samples for PK, ADA, biomarkers, as well as collection of data for patient-reported outcomes should be discontinued. The intent is to minimize the burden on study participants and site staff.

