### 5.1.1 FRACTION-Gastric Cancer Tracks 1 and 2 Design

A detailed study schematic for both Tracks 1 and 2 is presented in [Figure 5.1.1-1](#).

[figure not shown]
Participants who are naïve to anti-PD-1, anti-PD-L1, and anti-CTLA-4 treatment will be enrolled in Track 1, and they will be randomized to nivolumab in combination with ipilimumab or to one of the FRACTION-Gastric Cancer study treatment combinations. These participants will receive their assigned study treatment in Track 1 until completion of the Treatment Phase.

Participants who have received prior anti-PD-1, anti-PD-L1, or anti-CTLA-4 treatment will be enrolled in Track 2 and randomized to nivolumab in combination with ipilimumab, or to one of

the FRACTION-Gastric Cancer study treatment combinations. In addition, participants with PD who were treated in Track 1 or 2 and continue to fulfill all entry criteria may be enrolled in Track 2 and re-randomized to a new combination other than that previously received, if applicable. These participants will receive their assigned study treatment in Track 2 until completion of the Treatment Phase. The number of participants who initially enroll in Track 2 and those who enroll in Track 2 after treatment on Tracks 1 or 2 is described in [Section 10.1](#).

- **Participants with complete response (CR), PR, or SD** at the end of 2 years on Track 1 or 2 Treatment Phase will:
  - Enter safety follow-up and complete FU1, FU2, and FU3 visits
- **Participants with PD** during the Track 1 or 2 Treatment Phase will:
  - Enter safety follow-up and complete FU1, FU2, and FU3 visits
- **Participants with CR, PR, or SD who enter study follow-up and subsequently progress** will:
  - Enter safety follow-up and complete FU1, FU2, and FU3 visits

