### **5.1.3.3 Follow-up**

As of Protocol Amendment 06, tumor scans, survival status follow-ups, and collection of subsequent treatment information will end once the participant has disease progression or treatment discontinuation for any reason, whichever occurs first. Any assessments for monitoring of safety will continue per protocol until the final follow-up visit (FU3). Please refer to [Table 2-3](#).

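### Section 9.1 still puts a Week 24 limit on scheduled tumour assessments, which conflicts with the rule in Table 2-3 footnote c and Section 5.1.3.3 that scans run to progression or treatment discontinuation

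*Combined protocol and SAP*

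**What the plan says.** Section 9.1 (Efficacy Assessments) takes the assessment time points from the Sub-Protocols and adds its own end limit: "up to and including Week 24 during the Treatment Phase or until disease progression per RECIST v1.1 criteria". Treatment discontinuation and withdrawal follow in the same list. Nothing says whether the earliest or the latest item applies. The section then allows unscheduled scans: "Tumor assessments at other time points may be performed if the investigator is concerned about tumor progression".

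Table 2-3 footnote c, worded as of Protocol Amendment 06, says that tumour scans "will end once the participant has disease progression, or treatment discontinuation for any reason, whichever occurs first". Section 5.1.3.3 gives the same rule: scans "will end once the participant has disease progression or treatment discontinuation for any reason, whichever occurs first". Neither mentions Week 24.

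Sections 5.1 and 5.1.3.2 set a Treatment Phase of about 2 years. Section 5.1.1 classifies participants as CR, PR or SD "at the end of 2 years on Track 1 or 2 Treatment Phase".

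Section 9.1 refers to Section 2 for timing, but Section 2 has no on-treatment schedule: "The On-treatment Procedural Outline(s) and exceptions for study treatment combination arms are included in each" Sub-Protocol. The Sub-Protocols are not part of the supplied file.

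Median DOR is a primary endpoint (Table 4-1). Section 10.3.1 estimates it by Kaplan-Meier, counts progression or death as the event, and leaves the censoring rules to the SAP.

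**The concern.** A responder still on treatment at Week 30 keeps scheduled scans under footnote c and Section 5.1.3.3, but loses them if a site takes Week 24 in Section 9.1 as the last scheduled assessment. Two stated rules for when scans end therefore give different answers for the participants who determine DOR.

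If the Week 24 limit were followed, a response first seen at Week 8 could be followed by scheduled scans for only 16 weeks, and the Kaplan-Meier median would often be reported as not reached. Progression after Week 24 would be dated by scans that an investigator orders on suspicion in an open-label study. That could differ between arms, and it feeds the descriptive Track 1 PFS hazard ratio and median PFS in Section 10.3.1.

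**Working it through.** **1. The plan's own figures.** The point disputes no stated sample size, but the Simon boundaries fix the smallest responder counts at which efficacy would be considered. Exact binomial calculation for Track 1 (4/19, 15/54) gives early stopping 0.673, false positive rate 0.048, power 0.904 and expected n 30.4 and 51.6. The plan states 67%, 5%, 90%, 30.4 and 51.6. For Track 2 (1/21, 4/41) the results are 0.717, 0.046 and 0.902, against 72%, 5% and 90%. The designs reproduce. At the efficacy boundary, DOR rests on 16 responders in Track 1 and 5 in Track 2.

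**2. The passages side by side.**

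| Place | When scheduled scans end | Week 24 limit |
|---|---|---|
| Section 9.1 | Week 24, or progression, discontinuation or withdrawal; governing item not stated | Yes, on the literal reading |
| Table 2-3 footnote c | Progression or treatment discontinuation, whichever is first | No |
| Section 5.1.3.3 | Same as footnote c | No |
| Sections 5.1, 5.1.3.2 | Treatment continues for about 2 years (about 104 weeks) | Not mentioned |
| Section 5.1.1 | Response status used at 2 years (by implication only) | Not mentioned |

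**3. Size if Week 24 were applied.** The documents give no time to response, DOR distribution or discontinuation rate, so these are assumptions: first response at Week 8, exponential DOR, nobody stopping treatment early, and no events counted after the last scheduled scan.

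- Window: w = last scan week − week of first response. To Week 24, w = 24 − 8 = 16. To Week 104, w = 104 − 8 = 96.
- Chance that one response ends within the window: p = 1 − 2^(−w/m), where m is the true median in weeks.
- The median is reached if at least half of the k responders have an event: P(Bin(k, p) ≥ ceil(k/2)), that is, at least 8 of 16 or at least 3 of 5.

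| True median DOR | p, w = 16 | Reached, scans to Week 24 (k = 16 / 5) | p, w = 96 | Reached, scans to Week 104 (k = 16 / 5) |
|---|---|---|---|---|
| 3 months (13 wk) | 0.574 | 80% / 64% | 0.994 | over 99% / over 99% |
| 6 months (26 wk) | 0.347 | 15% / 23% | 0.923 | over 99% / over 99% |
| 12 months (52 wk) | 0.192 | 0.5% / 5% | 0.722 | 98% / 86% |

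**4. Sensitivity.**

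- *Week of first response.* With first response at Week 6 to 16 (w = 18 to 8) and scans to Week 24, the chance at a true 3 months is 89% to 15% with 16 responders and 71% to 23% with 5.
- *Discontinuation.* If 20% to 60% stop treatment within a year of first response and scans stop with it, the Week 104 figures at a true 6 months fall to over 99% down to 99% (16 responders) and 98% down to 89% (5). At 12 months they are 95% to 84% and 82% to 68%. The Week 24 figures at 6 months stay at 12–14% and 24–27%.
- *Scan interval.* A separate simulation with 8-weekly scans, 2,000 runs per setting and a true median of 26 weeks left the median unreached in 84% (16 responders) and 77% (5 responders) of runs with scans to Week 24. With scans to Week 104 it was unreached in 0%. This agrees with the table.

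**5. What is not affected.** The Simon boundaries count responses only, and the Week 24 scan is kept, so ORR and the 24-week PFS rate change little. The exception is a response first seen at or after Week 24, which needs confirmation at least 4 weeks later.

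**The case against.** The strongest reply is that the governing rule is already in the document. Section 9.1 refers timing to Section 2, and footnote c to Table 2-3, which is in Section 2, gives the stopping rule as of Amendment 06. Section 5.1.3.3 repeats it. Section 7.4.1 keeps tumour assessments going through dosing delays, and the Table 2-3 notes describe 12-weekly scans after treatment for participants without progression (now limited by footnote c). A gap from Week 24 to Week 104 on treatment would make little sense beside these.

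Most of this stands: continued scanning is the favoured reading, and Week 24 may be leftover wording. It does not remove the conflict. Section 9.1 is operative text with its own end limit. The Amendment 06 summary lists Section 9.1 among the sections it changed, so footnote c cannot be said to replace it simply by being newer.

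A second objection is that the percentages are largely assumed. That is correct. Only the responder counts come from the plan, so the figures show what the literal reading would do and do not estimate what happened.

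A reader might also infer that the Week 24 limit would make median DOR too short. The documents do not support that. Censoring at Week 24 alone gives a median that is not reached. A downward bias appears only if later events are counted while every other responder is censored at Week 24, and the censoring rule is left to the SAP. Under that construction everyone still at risk after Week 24 has an event, so one captured late event takes the curve to zero. With 16 responders and a true median of 52 weeks, the chance that a response ends 16 to 96 weeks after it starts is 2^(−16/52) − 2^(−96/52) = 0.530. If a share s of such events is captured, the chance of at least one is 1 − (1 − 0.530s)^16 = 0.58, 0.90 and 0.99 at s = 0.10, 0.25 and 0.50. The simulated chance of reaching the median is the same: 0.58, 0.90 and 0.99. The apparent bias therefore comes from the assumed censoring. With 5 responders its direction is not even certain.

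**Conclusion.** The point holds as an internal inconsistency. Section 9.1 is wrong as written, because its literal reading ends scheduled scans at Week 24 while footnote c and Section 5.1.3.3 carry them to progression or treatment discontinuation. Severity is minor to moderate: the rest of the document points to continued scanning, but the endpoint exposed is primary.

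The consequence is conditional on a site or Sub-Protocol applying Week 24 as the last scheduled scan. In that case, under the assumptions in the working, median DOR would probably go unreached at true medians of 6 months or more. At 3 months the result depends heavily on when the first response is seen.

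Two further inferences go beyond the documents. One is that scans actually stopped at Week 24; the Sub-Protocol schedules are not supplied, so practice cannot be seen. The other is that median DOR should be replaced as a primary measure; that would answer a reading which the document's other passages disfavour.

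**What to change.** Check the on-treatment schedule in each Sub-Protocol, then reconcile Section 9.1 with Table 2-3 footnote c and Section 5.1.3.3. In the phrase "up to and including Week 24 during the Treatment Phase or until disease progression per RECIST v1.1 criteria", delete everything up to and including the first *or*, and add a precedence rule. The sentence should then say that assessments continue at the Sub-Protocol's intervals until progression, treatment discontinuation or withdrawal, whichever is first. The same edit can deal with the wording on participants treated beyond progression, which remains in Section 9.1 although Section 7.4.2 is now marked not applicable.

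The cost is one phrase in the Master Protocol and a check of the Sub-Protocol schedules. No new procedures are needed where later scans are already scheduled, and no sample size, error rate or decision boundary changes.
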